2.3.2 Secondary Outcomes

- Change from baseline in SAQ and EQ-5D-5L scores at 3 months
- The rate of target vessel failure and its components (cardiac death, myocardial infarction, stent thrombosis, unplanned rehospitalisation with target vessel revascularisation) will be analysed at 3 months
- The proportion of patients with final post-PCI $\text{FFR} \leq 0.80$
- The proportion of patients with final post-PCI $\text{DPR} \geq 0.90$
- The proportion of patients with final post-PCI $\text{RFR} \geq 0.90$
- The proportion of patients with final post-PCI $\text{CFR} \geq 2.0$
- The proportion of patients with final post-PCI $\text{IMR} > 25$
- The proportion of patients with final post-PCI $\text{IMRc} > 25$
- ΔFFR from pre-PCI to final post-PCI value
- ΔDPR from pre-PCI to final post-PCI value
- ΔRFR from pre-PCI to final post-PCI value
- ΔCFR from pre-PCI to final post-PCI value
- $\Delta\text{Resting transit time (TT}_{\text{rest}}\text{)}$ from pre-PCI to final post-PCI value
- $\Delta\text{Hyperaemic transit time (TT}_{\text{hyp}}\text{)}$ from pre-PCI to final post-PCI value
- ΔIMR from pre-PCI to final post-PCI value
- ΔIMRc from pre-PCI to final post-PCI value
- ΔFFR from pre-PCI to final post-PCI value
- Percent FFR change from pre-PCI to final post-PCI value
- Percent DPR change from pre-PCI to final post-PCI value
- Percent RFR change from pre-PCI to final post-PCI value
- Percent CFR change from pre-PCI to final post-PCI value
- Percent TT_{rest} change from pre-PCI to final post-PCI value
- Percent TT_{hyp} change from pre-PCI to final post-PCI value
- Percent IMR change from pre-PCI to final post-PCI value

- Percent IMR_c change from pre-PCI to final post-PCI value
- Procedure Duration
- The cost of additional equipment employed in the experimental arm
- Fluoroscopy Dose
- Contrast Material Dose
- Incidence of procedural complications such as coronary artery dissection or perforation.
- An 'As Treated' analysis of the preceding primary and secondary outcome measures

For the binary categorical secondary outcomes, the same analysis approach will be used as with the primary outcome. For quantitative secondary outcomes, two sample t-tests and 95% CI will be used, as well as further analyses using regression to investigate whether any of the baseline characteristics affect the outcome. Given the sample size of 130 per group and large number of baseline characteristics, this will be performed by first investigating each characteristic on its own (together with the treatment group). Any variables that are significant here will be added to build a larger model, bearing in mind sample size limitations.

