- Recent (within 1 week prior to cardiac catheterization) ST-segment elevation myocardial infarction (STEMI) in any arterial distribution (not specifically target lesion).
- Severe cardiomyopathy (ejection fraction <30%).
- Renal insufficiency such that an additional 20 to 30 mL of contrast would, in the opinion of the operator, pose unwarranted risk to the patient.

Methods/Design:

Informed consent will be obtained prior to cardiac catheterisation in all potential subjects conforming to the inclusion and exclusion criteria.

Patients will then be randomised to one of two groups (described below) and PCI will be performed, using a pressure guidewire, according to standard practice at the Golden Jubilee National Hospital (including lesion pre-dilation and post-dilation of the stented segment).

Group 1 (PIOS Group):

Operator-blinded FFR will be measured post PCI.

If FFR is ≥ 0.90 , no further intervention will be performed and the procedure is considered complete.

If FFR is < 0.90 , the result will be disclosed to the operator and a hyperaemic pressure wire pullback during either a standard peripheral intravenous adenosine infusion (140mcg/kg/min) or an intracoronary adenosine infusion (360mcg/min) via a microcatheter will be performed. Depending on the result the operator would then have the following options:

- A. If there is a step-up of ≥ 0.05 across the stented segment(s) further post-dilatation with a 0.25 - 0.50mm larger non-compliant balloon to at least 18 atmospheres should be performed followed by repeat FFR. Alternatively, the operator may choose to employ intracoronary imaging (IVUS or OCT) to guide post-dilation/optimisation of the stented segment.

- B. If there is a step-up of ≥ 0.05 across a relatively focal (<20mm) unstented segment which is technically suitable for further stenting then a further stent should be implanted followed by repeat FFR.
- C. If the FFR remains < 0.90 after steps A +/- B, a further FFR pullback will be performed. If the criteria for Step B are again met, one additional stent may be deployed and a final FFR pullback performed. Following this, the FFR result will be accepted.
- D. If the residual pressure gradient is interpreted to reflect diffuse atherosclerosis with no focal step-ups, the result is accepted.

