- E. At the end of the procedure the pressure wire sensor will be withdrawn to the tip of the guiding catheter and compared with the aortic pressure. A pressure drift of ≤ 0.03 will be accepted and the final FFR result adjusted accordingly.
- F. If there is a drift of ≥ 0.04 , the wire should be re-equalised and the final FFR measurement be repeated.
- G. The patients will have their demographics and procedure details recorded. All patients will receive 3-month telephone follow-up.

Group 2 (Control Group):

Post PCI FFR will be recorded but not disclosed to the operator. The angiographically defined result will be accepted. The patients will have their demographics and procedure details recorded. All patients will receive 3-month telephone follow-up.

Primary Outcome

The primary end-point in this study will be the proportion of patients with a physiologically optimal result post PCI (FFR ≥ 0.90). We hypothesise that our PIOS intervention can increase the proportion of patients achieving this target from 40% to 60% and believe that an increment of at least this magnitude would be necessary to make a future larger study with both patient-oriented clinical (target vessel failure) and health care system (resource utilisation) outcomes acceptable to the interventional cardiology community and potential funders.

Secondary Outcomes

The main secondary outcome measure will centre on assessing change from baseline in self-reported health outcomes at 3 months using both generic and disease-specific quality of life measurement tools.

The EQ5D is a generic quality of life measurement tool which expresses preference for health status using a single index score and is the recommended tool by the National Institute for Health and Clinical Excellence (NICE) for calculation of Quality-Adjusted Life Years. It covers 5 dimensions of health: mobility, self-care, usual activities, pain/discomfort, and anxiety/depression.

The SAQ is a self-administered, disease-specific measure for patients with coronary artery disease that has previously been demonstrated to be valid, reproducible, and sensitive to

clinical change. The SAQ quantifies patients' physical limitations caused by angina, the frequency of and recent changes in their symptoms, their satisfaction with treatment, and the degree to which they perceive their disease to affect their quality of life.

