The rate of target vessel failure and its component features (cardiac death, myocardial infarction, stent thrombosis, unplanned rehospitalisation with target vessel revascularisation) will be analysed at 3 months.

Additional secondary outcomes including procedural/patient safety factors will also be measured. These would include: procedure time, fluoroscopy dose, contrast dose, complications and cost of additional equipment employed (balloons/stents/intra-coronary imaging).

Power calculations

Assuming (as per data from previous studies) that 40% of patients in the control arm have a post PCI FFR ≥ 0.90 and that it is considered clinically relevant if the equivalent percentage in the PIOS treatment arm is at least 60%, we will require a sample size of 130 per group to have 90% power to be able to detect a difference in the population in these proportions at the 5% significance level.

Expected value of results

1. Confirmation that the proposed PIOS protocol significantly increases the proportion of patients obtaining a physiologically optimal post PCI result will demonstrate the feasibility of this strategy and should lead to an increase in post PCI pressure wire usage to achieve physiologically optimal results for patients.
2. The secondary outcome measures, albeit underpowered for clinical outcomes in this study, will hopefully still give a signal that achieving a target post PCI FFR ≥ 0.90 does yield objective benefits for patients. This could then form the basis for a larger phase 3 trial to confirm improved clinical outcomes and cost-effectiveness of FFR targeted PCI

References

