2.2 Baseline Characteristics

Baseline characteristics will be summarised in the FAS as a whole and by treatment group. The following baseline characteristics will be reported:

- Demographics: age (years), sex (male, female), height, weight, BMI, ethnicity (White or White British, Asian or Asian British: South Asian, Asian or Asian British: Chinese, Asian or Asian British: Other Asian, Black or Black British, Mixed or Multiple, Other)
- Lifestyle Factors: Smoking Status (No, Current, Ex-Smoker <12 months, Ex-Smoker >12 months)
- Vital Sign Observations: heart rate, blood pressure
- Pharmaceutical therapy (medications used for treatment of cardiovascular disorders including primary and secondary therapies)
 - Number of antianginal medications
- Medical History including Risk Factors (yes/no unless otherwise stated)
 - Indication for Angiogram (Stable Angina, ACS-NSTEMI, ACS-Unstable Angina)
 - Time since NSTEMI
 - Troponin Assay Used and Peak Troponin Recorded if NSTEMI
 - Hypertension
 - Hypercholesterolaemia
 - Diabetes
 - TIA/Stroke
 - CKD
 - Thyroid Dysfunction
 - Pacemaker
 - ICD
 - Atrial Fibrillation
 - Heart Failure (No, HF-rEF, HF-pEF)
 - NYHA Class if Heart Failure (1-4)
 - Previous PCI
 - Previous MI
 - History of Previous MI in Target Vessel if Yes
 - CABG
 - Angina
 - Canadian Cardiovascular Society (CCS) Class if Angina (1-4)
 - Valvular Heart Disease
 - Valve Replacement/Repair
 - Family History of CAD
- Health Status questionnaire scores:
 - Seattle Angina Questionnaire
 - EQ-5D-5L
- Procedural Characteristics
 - Vascular Access (Radial, Femoral, Brachial)
 - Sheath Size

- Multivessel Procedure (Yes, No)
- Procedure Time
- Duration of Research Protocol
- Contrast Dose
- Dose Area Product
- Radiation Dose
- Total Duration of Adenosine Infusion
- Total Dose of Adenosine
- Total Number of Stents Deployed in Study Artery
- Total Length of Stents Used in Study Artery
- Diameter of Largest Balloon used for PCI
- Largest Stent Diameter

- Angiographic Characteristics
 - Target Coronary Artery Segment
 - Lesion Severity by Operator's Visual Assessment (Normal, Plaque Disease, <25%, 25-49%, 50-74%, 75-94%, >/= 95%, Subtotal Occlusion, Occluded)
 - AHA Lesion Type
 - Lesion APPROACH Score
 - Gensini Score
 - QCA Lesion Length
 - Pre- and Post-PCI QCA Diameter Stenosis
 - Pre- and Post-PCI QCA Area Stenosis
- Pre- and Post-PCI Coronary Physiology Test Results
 - Ratio of distal coronary to aortic pressure (Pd/Pa)
 - Diastolic Pressure Ratio (dPR)

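### Target vessel failure leaves out unplanned repeat revascularisation of the target vessel before discharge, an omission that could favour the PIOS arm

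*SAP*

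**What the plan says.** SAP 2.3.2 lists the TVF components as "cardiac death, myocardial infarction, stent thrombosis, unplanned rehospitalisation with target vessel revascularisation". The protocol, under Secondary Outcomes, gives the same four and ends "unplanned rehospitalisation with target vessel revascularisation) will be analysed at 3 months". Neither document adds a definition of any component.

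Other text bearing on the point:

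- **Treatment difference.** Under the protocol's Group 1 steps A to C, a PIOS patient whose first FFR is below 0.90 may have further post-dilatation and a further stent, after which "one additional stent may be deployed and a final FFR pullback performed". In Group 2 the operator is not shown the FFR and the angiographic result stands.
- **Other reporting of early harm.** SAP 2.3.2 has a separate item, "Incidence of procedural complications such as coronary artery dissection or perforation". SAP 2.5.3 summarises serious adverse events up to the 3-month follow-up by randomised group.
- **Follow-up.** The protocol states "All patients will receive 3-month telephone follow-up".
- **Vessel attribution of MI.** The SAP separates MI by vessel at baseline (2.2: "History of Previous MI in Target Vessel if Yes") but attaches no vessel to MI in the composite.
- **Role of TVF.** It is secondary here. The protocol (Primary Outcome) names it as the patient-oriented clinical outcome of a possible larger study, and SAP 2.8 foresees analyses of its predictors at 3 months and 1 year.

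**The concern.** The revascularisation component depends on how the patient reached the catheter laboratory, not on what happened to the vessel. Someone taken back for an unplanned procedure on the target vessel while still an inpatient fails the rehospitalisation condition. The same procedure at an unplanned readmission a few days later would count.

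The gap covers the index admission, when a mechanical complication of additional dilatation or stenting could appear. Only the PIOS strategy adds that treatment, so there is no reason to assume that uncounted events fall equally in the two arms. If more fall in the PIOS arm, its TVF rate looks better than it was. At stake is the between-arm TVF comparison, in an outcome the protocol hopes will give a signal for a later trial.

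A second, smaller gap is that the documents do not say whether MI in the composite means MI in the target vessel or any MI.

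**Working it through.** **1. The plan's own figure.** The documents give no rate, effect or power for TVF. Their only sample-size figure is for the primary outcome: 40% against 60%, 90% power, two-sided 5%. With pooled variance, n = [1.960 × √(2 × 0.5 × 0.5) + 1.282 × √(0.24 + 0.24)]² / 0.20² = (1.386 + 0.888)² / 0.04 ≈ 129.3, rounded up to 130 per group, as stated. That figure is not in question.

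**2. The definition applied to cases.**

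| Revascularisation of the target vessel within 3 months | TVF event as written? |
|---|---|
| At an unplanned readmission after discharge | Yes, fourth component |
| Unplanned, before discharge, with MI, stent thrombosis or cardiac death also recorded | Yes, through that component |
| Unplanned, before discharge, with none of these | **No** |

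The third row is the gap. Such a case may appear among serious adverse events or procedural complications, but neither list feeds the composite.

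**3. Direction.** Let m_P and m_C be the shares of true target vessel failures left uncounted in the PIOS and control arms. Then observed risk ratio = true risk ratio × (1 − m_P) / (1 − m_C). All inputs below are assumptions.

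- Equal shares: the risk ratio is unchanged and the risk difference shrinks. With 3% against 1.5% and a quarter missed in each arm, the rates become 2.25% and 1.125%. The ratio stays at 0.50 and the difference falls from 1.5 to 1.1 percentage points.
- Uncounted in PIOS only: with a true ratio of 1, m_P = 0.10 gives 0.90 and m_P = 0.25 gives 0.75, both in favour of PIOS.
- Uncounted in control only: with a true ratio of 1, m_C = 0.25 gives 1 / 0.75 = 1.33, against PIOS.

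The design makes the second pattern plausible. It does not establish it.

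**4. Size.** One uncounted patient in an arm of 130 moves its rate by 1/130 = 0.77 percentage points. If 0.5% to 2% of an arm had an in-hospital repeat revascularisation, that would be 0.005 × 130 = 0.65 to 0.02 × 130 = 2.6 patients. That range is an assumption, and it is a ceiling on the uncounted cases, because those with MI, stent thrombosis or cardiac death already count.

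**5. MI attribution.** If MI unrelated to the target vessel does count, at rate u in each arm, then observed risk ratio = (RR × p + u) / (p + u), where p is the control rate of target-vessel events. With assumed RR = 0.50 and u = 1%:

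- p = 2%: 0.020 / 0.030 = 0.67
- p = 3%: 0.025 / 0.040 = 0.63
- p = 5%: 0.035 / 0.060 = 0.58

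Power at 130 per group is 10% to 18% across these control rates with no unrelated MI, and 7% to 16% with u = 1%. It is low under either definition.

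**The case against.** The strongest reply is that early harm is not lost. Serious adverse events are summarised by arm with their relationship to study procedures, and the procedural complications item gives dissection and perforation only as examples. Keeping procedural harm apart from later vessel failure can be a deliberate choice. The components are also reported alongside the composite. This stands as far as it goes: a careful reader of the safety tables might find these cases. They would still be missing from the TVF comparison and from the revascularisation row itself, and neither document says that the restriction is deliberate.

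A reader might also infer more than the text supports:

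- **That all early repeat intervention is missed.** It is not. Unplanned readmission with target vessel revascularisation counts from discharge to 3 months, and inpatient reintervention with MI or stent thrombosis counts through those components.
- **That MI in any vessel counts.** This is inferred from silence. The baseline item on MI in the target vessel shows that the SAP can make the distinction, but the composite's name points the other way. The sure finding is that attribution is unspecified.
- **That a set fraction of events is lost.** The 40% at 3 years in the protocol's Background, taken as a constant hazard, gives 1 − 0.6^(1/12) = 4.2% at 3 months, or 5.4 events in 130. Against that, 0.65 to 2.6 patients would be 12% to 48%. But the 40% refers to death, MI or repeat revascularisation in the lowest tertile of post-PCI FFR, not to TVF in a whole arm, and the numerator has no source in the documents.
- **That planning for the future trial is bound to be wrong.** The protocol names TVF for that trial without adopting this definition, and separate components let planners see MI and revascularisation individually.

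**Conclusion.** The point holds in a narrow form. Followed exactly, both documents exclude from TVF an unplanned repeat revascularisation of the target vessel during the index admission unless MI, stent thrombosis or cardiac death is also recorded. Because the extra dilatation and stenting belong to the PIOS strategy alone, the omission could favour PIOS. That direction rests on the assumption that the extra treatment produces some such events before discharge, and more of them than occur in controls.

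No rate in the documents supports a size for the effect. What can be said is that each uncounted patient is worth about 0.8 percentage points in an arm of 130. The protocol itself calls clinical outcomes underpowered, and the primary outcome is untouched. The undefined MI component is secondary and needs clarifying under either reading. This is an inexpensive improvement to a secondary outcome, not a threat to the trial's main conclusion.

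**What to change.** In the protocol (Secondary Outcomes) and SAP 2.3.2:

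1. Replace the revascularisation component with: any unplanned target vessel revascularisation after the end of the index procedure, including during the index admission. Fix the end of the index procedure in the same way for both arms, so that the PIOS optimisation steps are not themselves counted as repeat intervention.
2. Report in-hospital and post-discharge events in separate rows, by arm.
3. Keep the version 1.0 composite as a sensitivity row.
4. State whether MI in the composite means target-vessel MI or any MI, define it (including how periprocedural MI is handled), and report all MI separately.

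Items 1 to 3 cost wording and one eCRF field for timing, with no added visits or patients; the small downside is a departure from the version 1.0 wording. Item 4 costs only wording if any MI is meant. If target-vessel MI is meant, it needs an attribution rule and source records, since the follow-up described is a telephone call and no adjudication is mentioned.

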1.6 Sample Size and Power

260 patients will be randomised.

Previous studies suggest that approximately 40% of patients in the control arm will have a post-PCI FFR ≥ 0.90 .(1-5)

This is in keeping with pilot data from our own institution where, among 50 patients who underwent post-PCI FFR assessment, an initial result ≥ 0.90 was achieved in only 16 /50 (32%).

It is hypothesised that the proposed PIOS intervention will increase the proportion of patients with a final post-PCI FFR ≥ 0.90 by approximately 20% compared to the control group. (a relative improvement of at least 50%).

A sample size of 130 patients per group would be required to have 90% power to detect a 20% absolute difference between groups at the 5% significance level.

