1.8.6 Software

Analyses will be carried out using SPSS Statistics, version 25 and R, version 3.4 or above.

2. Analysis

All applicable analyses will be 2-sided and will be performed using a 5% significance level. All confidence intervals presented will be 95% and two-sided.

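### Testing eight secondary outcomes as mean percent change keeps the 5% error rate but loses power and biases within-arm means upward; a baseline-adjusted final value would serve better

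*SAP*

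**What the plan says.** SAP 2.3.2 names eight percent changes from the pre-PCI to the final value: FFR, DPR, RFR, CFR, resting and hyperaemic transit time, IMR and IMRc. Typical entries are "Percent IMR change from pre-PCI to final post-PCI value" and "Percent FFR change from pre-PCI to final post-PCI value". The absolute change of the same eight measures is also listed.

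The analysis paragraph that follows states: "For quantitative secondary outcomes, two sample t-tests and 95% CI will be used". Regression on baseline characteristics is a further analysis, in which covariates reach the larger model only if significant. No log scale, rank method or baseline-adjusted main analysis is specified. The opening of SAP section 2 adds: "All applicable analyses will be 2-sided and will be performed using a 5% significance level".

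Three other parts of the SAP bear on the point:

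- Section 1.8.2 requires median, quartiles and range alongside the mean.
- Section 2.2 includes pre-PCI physiology among the baseline characteristics.
- Section 2.3 uses final values only as proportions beyond a threshold (FFR, DPR, RFR, CFR, IMR, IMRc). No outcome compares the final value as a continuous measure.

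**The concern.** Percent change puts a noisy pre-PCI reading in the denominator, which has two consequences.

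First, the scale is asymmetric. A patient going from 20 to 40 scores +100% and one going from 40 to 20 scores −50%. Their mean is +25%, although the pair as a whole has not moved. For a variable measure such as IMR, CFR or transit time, an arm mean may be read as physiological change when part of it comes from the scale.

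Second, the two arms share one pre-PCI distribution, and the optimisation strategy acts only on the final value. Dividing by the pre-PCI value therefore adds variance without adding signal. The SAP says the data could support a definitive phase 3 study, so a weak test that misses a real physiological effect has a cost. The same outcomes are repeated in the as-treated analysis.

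**Working it through.** **Plan's own figure.** The documents give no figure for the percent-change outcomes. The sample size they rest on is "A sample size of 130 patients per group would be required to have 90% power", for 40% against 60%. With pooled variance and a two-sided 5% level:

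n = [1.960·√(2·0.5·0.5) + 1.282·√(0.4·0.6 + 0.6·0.4)]² / 0.20² = (1.386 + 0.888)² / 0.04 ≈ 129.3, so 130. This reproduces, and 130 per arm is used throughout.

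**Assumed inputs.** The documents give no SDs or pre/post correlations for these measures. For the skewed measures (CFR, transit times, IMR, IMRc), values are taken as lognormal with log-SD s = 0.40–0.70 and correlation r = 0.2–0.5.

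**1. Within-arm mean with no true change.** E[post/pre] − 1 = exp(s²(1−r)) − 1.

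- s = 0.40, r = 0.5: exp(0.08) − 1 = +8.3%.
- s = 0.70, r = 0.2: exp(0.392) − 1 = +48.0%.

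The median stays at zero. For low-variability measures the rise is small: under 3% at a coefficient of variation of 0.20 or below (r = 0.3–0.7).

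**2. Between-arm error.** Both arms carry the same inflation under the null. Simulated type I error of the percent-change t-test lay between 4.1% and 5.7% in all runs.

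**3. Power for a true 20% lower value, skewed measures.** Large-sample formulas, with v = 2s²(1−r):

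- percent change: z = 0.20 / √[(e^v − 1)(1 + 0.8²)/130]
- log ratio: z = 0.2231 / [s·√(2(1−r))·√(2/130)]
- log-scale ANCOVA: z = 0.2231 / [s·√(1−r²)·√(2/130)]

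Power is Φ(z − 1.96). At s = 0.70, r = 0.2 the z values are 1.63, 2.03 and 2.62, giving 37%, 53% and 75%. The table gives simulated values for the first two scales and the formula for ANCOVA.

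| s | r | percent change | log ratio | log ANCOVA |
|---|---|---|---|---|
| 0.40 | 0.2 | 92% | 95% | >99% |
| 0.40 | 0.5 | 99% | 99% | >99% |
| 0.55 | 0.2 | 62–64% | 72–73% | 92% |
| 0.55 | 0.5 | 85% | 90% | 97% |
| 0.70 | 0.2 | 40% | 54% | 75% |
| 0.70 | 0.5 | 63% | 73% | 84% |

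**4. FFR.** The final-value SD comes from the tertile medians of 0.83 and 0.98 in the Protocol's Background: (0.98 − 0.83)/(2 × 0.9674) = 0.0775, assuming normality. The mean is set to match the SAP's statement that "approximately 40% of patients in the control arm will have a post-PCI FFR" of at least 0.90: 0.90 − 0.2533 × 0.0775 = 0.880.

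The pre-PCI mean (0.60–0.70), SD (0.10–0.15) and correlation (0–0.5) are assumed. PIOS patients below 0.90 gain 0.03 or 0.04. These shifts move the proportion at or above 0.90 from 40% to about 55% and 60%, so the larger one corresponds to the trial's own target. Simulated power:

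- percent change: roughly 7–40%
- absolute change: roughly 14–58%
- final value: roughly 56–84%

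Percent change was the weakest of the three in every setting.

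A hand check uses a second assumed setting: pre-PCI 0.60 (SD 0.15), final SD 0.06, r = 0.3 and a uniform final difference of 0.02. The SD of percent change is then 46 points, and the effect is about 0.02/0.60 = 3.3 points, or 0.07 SD. On the final value the same effect is 0.02/0.06 = 0.33 SD. Simulated power was 9% for percent change, 20% for absolute change and 81% for ANCOVA.

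**5. Influence of low pre-PCI values.** A change from 0.30 to 0.88 is +193%, and from 0.75 to 0.88 is +17%. For an FFR-like measure (assumed mean 0.60–0.70, SD 0.08–0.15), the lowest tenth of pre-PCI values carries 36–62% of the variance of percent change, against 22–29% for absolute change. For skewed measures with a coefficient of variation of 0.5–0.6, that share is 19–37%.

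**The case against.** The strongest defence is that the planned test compares randomised arms, so the scale's upward bias cancels. That stands. A reader might infer a false-positive risk, but the design and the simulated error rates rule it out.

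The SAP also has safeguards. Medians and quartiles are reported, and the median is free of the artefact. Absolute changes are listed for all eight measures, and the exploratory regression could include the pre-PCI value. These help interpretation, but they do not repair the test. The regression still has percent change as its dependent variable and admits covariates by significance. For FFR, the absolute change is itself weak.

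The power loss depends on assumptions. At log-SD 0.40 and r = 0.5 the choice of scale is immaterial, and the log scale is favoured partly because the data were simulated as lognormal. This limits the size of the claim. For FFR, whose simulation is not lognormal, percent change still came last.

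A reader might also take "Subtotal Occlusion, Occluded" in SAP 2.2 to mean that very tight lesions will dominate all eight outcomes. That list is a descriptive severity scale, which also includes normal vessels. It does not say how many such patients will enrol, and the lowest tenth's share of the variance approaches domination only for a widely spread FFR.

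**Conclusion.** The point holds as one about efficiency and interpretation. The between-arm t-tests on percent change are valid at 5%, but in the settings examined they had at best equal and usually lower power than the log ratio for skewed measures. For FFR they were the weakest of the three scales. The within-arm means of the high-variability measures are biased upward by about 8% to 48% under no change.

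All sizes rest on assumed SDs and correlations. The no-change figure is a reference case: both arms undergo PCI between the readings, so any real change is mixed with the bias, and the documents do not show that reported arm means will be pure artefact. Nor do they support a prediction that the percent FFR outcome will look null if the strategy works. Power is low, but it reaches about 40% in the more favourable settings.

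The primary outcome, its analysis and the 130 per group are unaffected.

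**What to change.** In SAP 2.3.2, make the between-arm test for each of the eight measures a comparison of the final post-PCI value adjusted for its own pre-PCI value (ANCOVA). For FFR, DPR and RFR use the original scale. For CFR, both transit times, IMR and IMRc use the log scale, reported as a ratio of geometric means with 95% CI and stated as a percent difference. The percent reading is thereby kept.

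Keep percent change as descriptive only, by median and quartiles, without a t-test. Moving to an unadjusted log ratio, or simply dropping percent change in favour of absolute change, would recover only part of the power.

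The cost is SAP wording, slightly more analysis work and a ratio-scale effect for five measures. The data and software are those already planned. The Protocol's Secondary Outcomes section does not name these outcomes, so the wording to change is in the SAP alone.

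### SAP 2.3.2 compares absolute-change outcomes by valid but unadjusted t-tests; naming a model with the outcome's own baseline as the reported effect would usually be more precise at almost no cost

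*SAP*

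**What the plan says.** The protocol (Secondary Outcomes) states: "The main secondary outcome measure will centre on assessing change from baseline in self-reported health outcomes at 3 months". SAP section 2.3.2 lists "Change from baseline in SAQ and EQ-5D-5L scores at 3 months" and absolute changes from pre-PCI to final post-PCI value in FFR, dPR, RFR, CFR, resting and hyperaemic transit time, IMR and IMRc. That makes eight distinct measures, since ΔFFR is listed twice. Percent change in the same eight is listed separately.

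The closing paragraph of 2.3.2 gives the only analysis rule for quantitative secondary outcomes: "For quantitative secondary outcomes, two sample t-tests and 95% CI will be used, as well as further analyses using regression". The regressions have a stated purpose: "further analyses using regression to investigate whether any of the baseline characteristics affect the outcome". They begin by "first investigating each characteristic on its own (together with the treatment group"), and characteristics found significant then go into a larger model.

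The own-baseline values are available. SAP section 2.2 lists baseline SAQ and EQ-5D-5L scores and "Pre- and Post-PCI Coronary Physiology Test Results". The same list also holds items measured during or after the procedure, such as "Total Number of Stents Deployed in Study Artery".

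**The concern.** A t-test on change subtracts the whole baseline value, so it fixes the slope on baseline at 1. ANCOVA estimates that slope from the data. Both target the same treatment difference in a randomised trial, but the t-test's confidence interval is usually wider than the collected data require.

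Precision matters here because the protocol (Expected value of results) accepts that power is limited and still hopes to learn from these measures: "The secondary outcome measures, albeit underpowered for clinical outcomes in this study, will hopefully still give a signal". That hope concerns benefit to patients, so it bears most directly on SAQ and EQ-5D-5L and less on the physiological changes.

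**Working it through.** **The plan's own figure.** The only sample size given is for the primary outcome: 40% against 60%, two-sided 5%, 90% power. The pooled formula gives n = [1.960 × √(2 × 0.5 × 0.5) + 1.282 × √(0.24 + 0.24)]² / 0.20² = (1.386 + 0.888)² / 0.04 ≈ 129.3, so 130 per group as stated. No figure is given for any change outcome.

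**Inputs.** From the documents: 130 per arm, 1:1 allocation, two-sided 5%. Assumed, because the documents do not give them: the correlation r between baseline and follow-up, and k = baseline SD / follow-up SD.

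**Formulae.** Per-patient variance, in units of the follow-up variance:

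- t-test on change: k² + 1 − 2rk
- ANCOVA on own baseline: 1 − r²
- difference: (k² + 1 − 2rk) − (1 − r²) = (k − r)², which is never negative and is zero only when r = k
- ratio, ANCOVA to t-test: (1 − r²) / (k² + 1 − 2rk), which is (1 + r)/2 when k = 1

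**Equal SDs (k = 1).** The SE reduction is 1 − √ratio. The number of patients the t-test needs to match ANCOVA on 260 is 260/ratio.

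| r | Variance ratio | SE lower by | t-test patients to match 260 |
|---|---|---|---|
| 0.3 | 0.65 | 19% | 400 |
| 0.5 | 0.75 | 13% | 347 |
| 0.7 | 0.85 | 8% | 306 |
| 0.9 | 0.95 | 2.5% | 274 |

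**Unequal SDs.**

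- k = 2, r = 0.3: 0.91/3.8 = 0.24
- k = 1.5, r = 0.3: 0.91/2.35 = 0.39
- k = 0.75, r = 0.7: 0.51/0.5125 = 0.995
- k = 0.5, r = 0.5: 0.75/0.75 = 1.00, no gain

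The extra parameter multiplies the ANCOVA variance by about 1 + 1/256, a cost of about 0.4%.

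**Simulation.** This used 10,000 trials of 130 per arm per scenario. With k = 1, the empirical SE fell from 0.147 to 0.118 at r = 0.3, from 0.124 to 0.108 at r = 0.5 and from 0.096 to 0.089 at r = 0.7, as the formula predicts. Both methods were unbiased, with type I error between 4.8% and 5.1%.

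**The endpoint does not change.** If follow-up = a + τ × treatment + b × baseline, then change = a + τ × treatment + (b − 1) × baseline. The treatment effect τ is the same in both.

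These figures apply to absolute change only. They do not cover percent change, or outcomes with no baseline value such as procedure duration and contrast dose.

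**The case against.** The strongest reply is that the SAP already plans this model. Section 2.3.2 commits to fitting each baseline characteristic with treatment group, and own-baseline values are in the section 2.2 list. Treatment plus own baseline will therefore be fitted before any selection by significance. That is correct and lowers the weight of the point: what is missing is a designation, not an analysis. The gap remains because the regressions are there to see which characteristics matter. The SAP does not name any of them as the reported treatment effect, and the larger model built from them is a different model.

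A second reply is that the gain is unknown and may be small. This also stands. The assumed scenarios run from a variance ratio of 0.24 to 1.00. Nor would ANCOVA rescue a weak comparison. With k = 1 and r = 0.5, an effect that the t-test detects with 80% power is detected with 90%, but one at 20% rises only to 25%. The documents state no power for these outcomes, so both starting points are illustrative.

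A reader might go further and infer that the post-procedural items in section 2.2 will distort the reported treatment effect. The documents do not support this. The reported comparison is the t-test, which uses no covariates, and the SAP does not say that the larger model will report the effect. The presence of those items is only a reason to word the fix carefully.

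**Conclusion.** The point holds as a matter of precision and pre-specification. In large samples ANCOVA on own baseline is never less precise than the planned t-test, apart from about 0.4% in variance when r = k. At equal SDs the gain in SE runs from about 19% (r = 0.3) to 2.5% (r = 0.9). All of this rests on assumed correlations and SD ratios.

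It would be wrong to conclude that the t-tests are biased or invalid: randomisation protects them and simulation confirms nominal type I error. Nothing here calls the percent-change outcomes into question, since the figures do not apply to them. The primary analysis and the sample size of 260 are untouched. It is a modest improvement worth making because it is nearly free.

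**What to change.** In SAP section 2.3.2, for each absolute-change outcome (each SAQ score to be reported, EQ-5D-5L, and each of the eight Δ physiology measures):

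- Name one model in advance as the reported treatment effect with 95% CI. It is the follow-up or final value, or equivalently the change, on treatment plus that outcome's own baseline or pre-PCI value, kept whatever its significance.
- Keep the two-sample t-test as supportive.
- Use no post-PCI or strategy-affected item from section 2.2 as a covariate in this model. Pre-PCI physiology is eligible even if recorded after randomisation: it precedes the PCI, and by design the arms diverge only after the first post-PCI FFR (protocol, Methods/Design; SAP 1.5).
- Label the screening regressions exploratory.
- Leave the percent-change outcomes as listed.

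The cost is SAP wording and one degree of freedom per model. No new data are needed, the change-from-baseline endpoint is kept, and a patient without a baseline value is already missing from a change score.
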